# 9.2. Efficacy Analysis

Analgesic effect analyses will be performed using all available in-clinic pain intensity data from the safety population (see Section 9.4). The baseline pain intensity score will be the score from the in-clinic assessment at Visit 2.

Pain intensity scores will be summarized descriptively by study week and phase of the Treatment Period (Conversion/Titration Phase and Maintenance Phase). Actual scores and the change and percentage change from baseline will be calculated.

Rescue medication or additional analgesic medication use over time will be summarized descriptively.

# 9.3. Pharmacokinetic Analysis

# 9.3.1. Pharmacokinetic Analysis Datasets

The PK concentration population will be defined as all subjects with at least 1 plasma concentration measurement in this study. The PK analysis population will be defined as all pediatric subjects who have usable PK data (ie, data for which the relationship between the time of dose time of sampling can be determined) and are included in the estimates of the primary pharmacokinetic parameters of interest.

### 9.3.2. Pharmacokinetic Endpoints

Primary PK endpoints will include estimates of morphine  $C_{ss,av}$  and CL/F. Secondary PK endpoints will include Vz/F of morphine, data permitting. The exposure levels of the metabolites of morphine M3G and M6G, naltrexone, 6- $\beta$ -naltrexol following multiple dose treatment with PF-06412528. Graphical representations and regression analyses may be used to characterize the dose-exposure relationships for morphine, naltrexone, and 6- $\beta$ -naltrexol (data permitting).

#### 9.3.3. Pharmacokinetic Analysis

Given the expected very low fluctuation in steady-state morphine concentrations following PF-06412528 BID dosing in children based on PF-06412528 study ALO-KNT-202 in adults, the concentrations observed during the maintenance phase will be used as an estimate of  $C_{ss,av}$  of morphine and its metabolites (data permitting) in pediatric subjects. The CL/F of morphine will be estimated using a ratio of the daily dosing rate of PF-06412528 and the estimates of morphine  $C_{ss,av}$  in the Maintenance Phase. The concentration-time dataset will be analyzed to obtain estimates for Vz/F of morphine in pediatric subjects, data permitting. Covariates of interest (PF-06412528 dosage, age, body weight, gender, concomitant medications etc) will be assessed for their ability to account for the observed variability in morphine  $C_{ss,av}$ .

The observational data will be summarized using descriptive statistics (mean, standard deviation, median, minimum, and maximum) for the study group as a whole. Data permitting, graphical representations and regression analyses may be used to characterize the dose-exposure relationships for morphine, naltrexone, and 6-β-naltrexol.

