#### Pharmacokinetic Analysis

Given the very low fluctuation in steady-state morphine concentrations following PF-06412528 BID dosing, the concentrations observed during the Maintenance Phase will be used as an estimate of  $C_{ss,av}$  of morphine and its metabolites (data permitting) in pediatric subjects. The CL/F of morphine will be estimated using a ratio of the daily dosing rate of PF-06412528 and the estimates of morphine  $C_{ss,av}$  in the Maintenance Phase. The concentration-time dataset will be analyzed to obtain estimates for Vz/F of morphine in pediatric subjects, data permitting. Covariates of interest (PF-06412528 dosage, age, body weight, gender, concomitant medications etc) will be assessed for their ability to account for the observed variability in morphine  $C_{ss,av}$ .

The observational data will be summarized using descriptive statistics (mean, standard deviation, median, minimum, and maximum) for the study group as a whole. Data permitting, graphical representations and regression analyses may be used to characterize the dose-exposure relationships for morphine, naltrexone, and 6-β-naltrexol.

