#### 4.1. Inclusion Criteria

Subject and caregiver eligibility should be reviewed and documented by an appropriately qualified member of the investigator's study team before subjects and caregivers are included in the study.

Subjects must meet all of the following inclusion criteria to be eligible for enrollment into the study:

- 1. Subjects between the ages of 7 and 17 years, inclusive, at the time of enrollment.
- 2. Having confirmed moderate-to-severe pain requiring around-the-clock treatment with an opioid analgesic.
- 3. Be an experienced opioid user, defined as any subject treated with opioid therapy, equivalent to ≥20 mg per day of morphine, for a period of 3 consecutive days immediately prior to first day of dosing with PF-06412528.
- 4. Have parental/guardian (or adult caregiver) capable of providing informed consent, supervising the storage and administration of study drug, and complying with scheduled visits, treatment plan, and all other study procedures (see Section 4.4).
- 5. Evidence of a personally signed and dated informed consent document indicating that the subject's parent or legal/parental/guardian (eg, caregiver) has been informed of all pertinent aspects of the study. Subjects will be required to provide assent in compliance with local regulations and Institutional Review Board (IRB) requirements.
- 6. Male subjects able to father children and female subjects of childbearing potential who are sexually active and at risk for pregnancy must agree to use a highly effective method of contraception throughout the study and for at least 28-days after the last dose of PF-06412528.
- 7. Subjects who are willing and able to comply with scheduled visits, treatment plan, laboratory tests, and other study procedures.

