# 5.3. Study Drug Supplies

#### 5.3.1. Dosage Form(s) and Packaging

PF-06412528 (morphine sulfate and naltrexone hydrochloride extended release capsules) is a Schedule II (CII) oral dosage form available in the following strengths: 20 mg/0.8 mg, 30 mg/1.2 mg, 50 mg/2 mg, 60 mg/2.4 mg, 80 mg/3.2 mg, and 100 mg/4 mg. For purposes of this study, both a 10 mg/0.4 mg capsule and a 15 mg/0.6 mg capsule will be developed to meet the therapeutic needs of younger (lower weight) children. All PF-06412528 study drug, including the newly developed 10 mg/0.4 mg and 15 mg/0.6 mg capsule strengths, will be supplied by the Sponsor.

PF-06412528 study drug will be packaged and provided for use according to the total daily dose requirements of a subject as listed below:

Morphine Sulfate Total Daily Dose	Dosing Schedule	Capsule (dosage form)	Conversion/ Titration Phase Bottle Fill count (capsules/bottle)	Maintenance Phase Bottle Fill count (capsules/bottle)
10 mg	10 mg QD	CCI	10	20
15 mg	15 mg QD		10	18
20 mg	10 mg BID		20	36
30 mg	15 mg BID		20	36
40 mg	20 mg BID		20	36
60 mg	30 mg BID		20	36
80 mg	2x20 mg BID		40	72
100 mg	50 mg BID		20	36
120 mg	60 mg BID		20	36
160 mg	80 mg BID		20	36
200 mg	100 mg BID		20	36

No other medications, including rescue medications, will be supplied by the Sponsor.

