#### **5.4.** Administration

PF-06412528 is to be administered with or without food, as per the investigator's Brochure. The bottle label will direct the subject to take either QD or BID depending on the total daily dose requirement for that subject (eg, children of low weight may be assessed to start with the 10 or 15 mg dose QD. Those labels will indicate QD dosing. Dosing strengths greater than 15 mg will indicate BID dosing). When given BID, one dose must be administered in the morning and the second dose is to be administered approximately 12 hours later. Morning doses should be encouraged to be administered daily between 6:00-10:00 AM throughout the study. As a general rule, the initial calculated daily dosage of PF-06412528 should be reduced by 50% and then titrated to achieve a stable dose. When converting to PF-06412528, the investigator should consider the potency, route of administration, and total daily dose of the discontinued opioid(s), the medical status of the subject, the subject's degree of opioid experience and tolerance, the type and severity of chronic pain, and the use of concomitant rescue medications to control the pain. Because

steady-state plasma concentrations are approximated within 24 to 36 hours, PF-06412528 dosage adjustments may be done as frequently as every 1 to 2 days. Study drug will be dispensed to the subject's caregiver only.

When PF-06412528 extended-release capsules are administered whole, the naltrexone remains intact and does not affect the analgesic potential of morphine. However, if the capsule is crushed, chewed or dissolved, the naltrexone component is released, competitively binds at the mu-opioid receptors, thus inhibits the effects of the opioid.

Therefore, PF-06412528 extended-release capsules are to be swallowed whole. The pellets in the capsules are not to be crushed, chewed, or dissolved prior to swallowing.

The co-ingestion of PF-06412528 with alcohol could result in an increase in morphine plasma levels and potentially fatal overdose of morphine. Subjects should not consume alcoholic beverages or use prescription or non-prescription products containing alcohol while on PF-06412528 therapy.

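### The ratio-based Css,av and CL/F rest on low fluctuation under BID dosing but are applied to all children, although 10 and 15 mg/day are supplied QD through Maintenance

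*Protocol*

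**What the plan says.** Css,av and CL/F of morphine are the primary PK endpoints (Protocol sections 2.2.1 and 9.3.2). Section 9.3.3 justifies using observed concentrations as Css,av with "Given the expected very low fluctuation in steady-state morphine concentrations following PF-06412528 BID dosing in children", citing an adult study. The Protocol Summary gives the same ground: "Given the very low fluctuation in steady-state morphine concentrations following PF-06412528 BID dosing". Then "The CL/F of morphine will be estimated using a ratio of the daily dosing rate of PF-06412528" and the Css,av estimates. The results are "summarized using descriptive statistics (mean, standard deviation, median, minimum, and maximum) for the study group as a whole". The PK analysis population in section 9.3.1 is not limited by regimen. The covariates named in section 9.3.3 include dosage, age and body weight, but not dosing interval.

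Not every child is on BID dosing. Under section 5.3.1 study drug is "packaged and provided for use according to the total daily dose requirements of a subject as listed below", and the table lists 10 and 15 mg/day as QD, with Maintenance bottles of 20 and 18 capsules. Every daily dose from 20 mg up is BID. The 10 and 15 mg strengths were added "to meet the therapeutic needs of younger (lower weight) children", and section 5.4 says that "children of low weight may be assessed to start with the 10 or 15 mg dose QD".

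For sampling, section 7.5.1 asks for two samples at Visit 4, at least 2 hours apart, with clock times recorded. It sets no post-dose window.

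**The concern.** The reason given for equating an observed concentration with the steady-state average is specific to a 12-hour interval. Doubling the interval at the same daily dose widens the peak-to-trough swing, and the protocol neither extends its premise to QD nor says what to do with QD children. Because CL/F is a ratio, any error in Css,av passes straight into it.

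What is at stake is less the pooled mean than where the error sits. In the supply table QD is the only schedule at the two lowest daily doses, and low-weight children are the protocol's own example for QD starts. Section 9.3.3 tests dosage, age and body weight against Css,av. A dosing-interval artefact could therefore be read as a dosage or weight effect. Entering dosage as a covariate cannot separate the two, because regimen and lowest dose coincide.

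**Working it through.** The documents give no fluctuation figure for either regimen, so there is nothing to reproduce. The check has four parts.

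**1. Is QD provisioned up to PK sampling?** Maintenance supply is capsules divided by capsules per day: 10 mg QD 20/1 = 20 days; 15 mg QD 18/1 = 18 days; single-capsule BID rows 36/2 = 18 days. Visit 4 comes two weeks after a stable dose is reached (section 3.2.1). QD is therefore provisioned through the sampling visit.

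**2. How much wider is QD fluctuation?**

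Inputs:
- Elimination half-life 2.3 h (Protocol section 1.3, from other oral morphine products), so ke = ln2/2.3 = 0.301/h.
- Absorption half-life 4-12 h. This is an assumption; the documents give none.
- One compartment with first-order absorption, which is the SAP's initial structural model (SAP 8.2.2).

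Scaled so that Css,av = 1:

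`C(t) = ke·tau · ka/(ka - ke) · [exp(-ke·t)/(1 - exp(-ke·tau)) - exp(-ka·t)/(1 - exp(-ka·tau))]`

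Example with 8 h absorption (ka = 0.0866/h), at trough (t = 0):
- QD: 7.23 × (-0.4035) × (1.0007 - 1.1429) = 0.41
- BID: 3.62 × (-0.4035) × (1.0276 - 1.5469) = 0.76

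The corresponding peaks are 1.52 and 1.15, so fluctuation (peak minus trough, over the average) is 110% for QD and 39% for BID. A lag time shifts the curve but leaves fluctuation unchanged.

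For one child, take two samples 2 h apart and average them (an assumption, since section 9.3.3 does not say how they combine). Then estimated/true CL/F = 1 / [(C(t) + C(t+2))/2].

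| Absorption half-life | Fluctuation QD | Fluctuation BID | QD/BID | CL/F ratio, any time in interval: QD | BID |
|---|---|---|---|---|---|
| 4 h | 189% | 73% | 2.6 | 0.50-5.63 | 0.79-1.53 |
| 6 h | 140% | 51% | 2.7 | 0.60-2.99 | 0.85-1.32 |
| 8 h | 110% | 39% | 2.8 | 0.67-2.21 | 0.88-1.22 |
| 12 h | 77% | 26% | 2.9 | 0.75-1.65 | 0.92-1.14 |

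The last two columns are outer limits. With the sampling span in SAP 2.1 (first sample 0-9 h after the morning dose, second 2 h later) and no lag, the QD span narrows to 0.67-1.23 at 8 h and 0.75-1.20 at 12 h. With a 2 h lag the full QD span returns.

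**3. Is there a stable average bias?** No. With the SAP span and first-sample times uniform over 0-9 h, understatement of QD CL/F across the 4-12 h absorption range is:

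| Assumed lag | 1 - mean(1/C) | 1 - 1/mean(C) |
|---|---|---|
| 0 h | 18 to 39% | 19 to 41% |
| 1 h | 13 to 33% | 15 to 39% |
| 2 h | 5 to 11% | 10 to 34% |
| 3 h | -4 to -40% (overstated) | 4 to 25% |

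Over the same lags BID runs from about 1% overstated to 8% understated.

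**4. What reaches the pooled result?** Shift = QD share × (1 - CL_QD/CL_BID). For a 10% share, 8 h absorption and no lag: 0.10 × (1 - 0.751/0.964) = 2.2%. The QD share is not in the documents. For assumed shares of 5%, 10% and 20%, with lags of 0-2 h, pooled CL/F is 0.2-1.8%, 0.4-3.6% and 0.7-7.2% below the q12h-only value. With absorption of 8-12 h only, the upper ends fall to 1.1%, 2.3% and 4.6%. With a 3 h lag and the mean of ratios the sign flips: at 10% and 4 h absorption, 0.10 × (1.40/1.013 - 1) = 3.8% above.

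The share is probably low. Entry requires opioid therapy equivalent to at least 20 "mg per day of morphine, for a period of 3 consecutive days immediately prior to first day of dosing", while QD means 15 mg/day or less. In Appendix 2, 8 of 37 conversion rows start QD (1/5 fentanyl, 2/5 hydrocodone, 2/6 hydromorphone, 0/7 methadone, 1/5 morphine, 1/6 oxycodone, 1/3 oxymorphone). These rows convert 20-32 mg/day morphine equivalent at about half dose, and titration follows. This counts table rows, not children.

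**The case against.** The strongest reply is that the plan already has a method that copes with QD. Section 2.2.1 still calls the primary endpoints population PK estimates, section 9 leaves detailed methodology to the SAP, SAP 8.2.2 specifies nonlinear mixed-effects modelling, and SAP 7.3 uses actual sampling times. Such a model can take dosing interval into account. This stands in part, and it would be too strong to infer that the documents offer no means of handling QD children. But the SAP still lists Vd/F as a primary PK endpoint and a Visit 8, neither of which matches Amendment 2. Section 9 also sends major changes to a primary analysis to a protocol amendment. The documents do not say which method yields the reported CL/F, and the ratio method as written has no rule for QD.

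Second, QD may be mostly a starting regimen. Bottle counts show provision, not use. That stands, and it limits the size.

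Third, dosage is a named covariate, so QD children are identifiable if the section 5.3.1 schedules are followed. True, but identifying them does not correct the estimator or separate regimen from low dose.

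Fourth, the absorption range is assumed, and its 4-6 h end gives BID fluctuation of 51-73%, hardly very low. That also stands; the 8-12 h rows fit the protocol's premise better. At 16 h absorption fluctuation is still 59% for QD against 20% for BID, so the contrast between regimens does not depend on the choice.

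**Conclusion.** The gap is real but minor. The premise in section 9.3.3 covers BID dosing, the estimator is applied to everyone, and the protocol supplies a QD regimen through PK sampling. For any QD child the ratio estimate is much more sensitive to sampling hour, with fluctuation 2.6 to 2.9 times that under BID. That finding rests on the one-compartment model and the assumed absorption range, but not on lag.

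Two stronger readings are tempting and are not supported. A reader might infer that CL/F is systematically understated in QD children; the average error shrinks or reverses with an assumed lag, so its direction is unknown. A reader might also infer that the pooled primary PK results are materially wrong. The number of QD children is unknown and probably small, the pooled shift is likely a few percent at most, and the study is descriptive with no decision rule (SAP 4.1 and 4.2). What remains is a risk of misreading at the lowest doses, which data already collected can largely remove.

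**What to change.** In section 9.3.3 and the matching Protocol Summary text:

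- Keep all children in the analysis. Making q12h children the only main estimate would drop the lowest-dose children from a study meant to describe ages 7 to 17.
- Report ratio-based Css,av and CL/F separately for q12h and QD children, with the number in each group and sampling times after dose.
- Show the pooled result with and without QD children as a sensitivity analysis.
- Include dosing interval as a flag or covariate in the Css,av covariate analysis and in any dose-exposure regression.
- If the population model is run, use recorded dose and sample times for all children.

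No new data are needed. Dosing frequency is recorded at each visit (section 3.2.1), and the morning dose, the previous three doses and the sample times are recorded at Visit 4 (section 6.2.2). The cost is a few lines of text and a little more analysis. If the sponsor regards this as a major change to a primary analysis, section 9 requires a protocol amendment. The drawback is that the QD summary may rest on very few children.

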### 9.4. Safety Analysis

One safety population is planned consisting of all subjects who participate in the Treatment Period and receive at least one dose of PF-06412528.

Safety data will be summarized for the Safety population.

#### 9.4.1. Adverse Events

All AEs will be coded to System Organ Class and Preferred Term (using MedDRA®). Treatment-emergent AEs will be defined as AEs that commence on or after the start of PF-06412528 administration. Subjects who have multiple events in the same System Organ Class and Preferred Term in a period will be counted only once at each level of summation (overall, by System Organ Class, and by Preferred Term).

Treatment-emergent AEs will be summarized separately for the Conversion/Titration Phase and the Maintenance Phase (including up to End of Study) by System Organ Class, Preferred Term, maximum intensity, and highest relationship to study drug.

Serious AEs and those leading to study withdrawal will be summarized.

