#### 2.2. Endpoints

### **2.2.1. Primary**

- *Safety:* incidence, intensity, relationship, and seriousness of adverse events (including symptoms of opioid toxicity or withdrawal) during treatment with PF-06412528.
- *Pharmacokinetics:* population pharmacokinetic estimates of morphine apparent clearance (CL/F) and average steady-state concentration (Css,av) following treatment with PF-06412528.

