#### 3. STUDY DESIGN

[figure not shown]
This is a multicenter, 6-week, open-label, single-arm study to demonstrate the safety and characterize the PK of PF-06412528 in children 7 to 17 years of age, with moderate-to-severe pain.

Subjects must be taking opioids prior to entry into the study. Initial PF-06412528 dosage will be determined by the subject's pre-study opioid treatment prior to the Conversion/Titration Period.

The study consists of 3 study periods (Figure 1) including:

- Screening Period (Visit 1) lasting up to 2 weeks.
- Treatment Period (Visits 2-6) lasting up to 10 weeks.
- Post-Treatment Period/End of Study Period (Visit 7) lasting 1 week.

Figure 1. Overall Study Design

The study will enroll approximately 140 children between the ages of 7 and 17 years with at least 100 subjects exposed to study treatment for at least 2 weeks in the Maintenance Phase. Plasma samples will be collected at 2 time points under steady-state conditions from each subject in the two age groups (7-11 years and 12-17 years) to characterize the pharmacokinetics of morphine and determine the systemic exposures of M3G, M6G, naltrexone and 6-β-naltrexol.

Opioid naïve subjects will not be enrolled in the study.

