# 3.2.2. Maintenance Phase (Visit 4-6)

The goal of the Maintenance Phase is to characterize the PK under steady-state study conditions as well as demonstrate the safety of PF-06412528 over a 2-6 week period. If at Visit 4 subjects require additional pain relief in the opinion of the investigator, they will continue in the study for an additional 2-4 weeks (Visit 5 and/or Visit 6) up to 6 weeks total.

Daily Diary and in-clinic pain intensity and safety will be assessed at each visit to determine if any dose adjustments are required. Rescue medication (acetaminophen and/or NSAID's) is permitted during this phase. IR morphine for rescue is discouraged during the Maintenance Phase.

Blood samples will be collected for PK analysis at Visit 4 for those subjects that achieve a stable dose between Visits 3a-d. Two blood samples will be taken at least two-hours apart at Visit 4. If for any reason PK samples are not obtained at Visit 4, the subject should return to enable them to be obtained at an unscheduled visit.

At the final Maintenance Phase visit (Visit 4 or 5 or 6), the investigator will discontinue the subject's PF-06412528 therapy and convert the subject back to their standard of care of opioid therapy. Blood samples will be collected for PK analysis if not already obtained. A Post-Treatment/End of Study visit will be scheduled in 7 ±2 days (Visit 7).

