6. ENDPOINTS AND COVARIATES

6.1. Safety Endpoints

6.1.1. Primary

Incidence, intensity, relationship, and seriousness of adverse events (including symptoms of opioid toxicity or withdrawal) during treatment with PF-06412528.

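### The Maintenance-phase adverse-event column runs past the last dose to End of Study, so it pools off-drug events with the on-treatment events that the primary endpoint names

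*Protocol*

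**What the plan says.** - **Endpoint.** Protocol 2.2.1 defines primary safety by "adverse events (including symptoms of opioid toxicity or withdrawal) during treatment with PF-06412528". SAP 6.1.1 agrees: "Incidence, intensity, relationship, and seriousness of adverse events (including symptoms of opioid toxicity or withdrawal) during treatment with PF-06412528".
- **Treatment-emergent AE.** Protocol 9.4.1: "Treatment-emergent AEs will be defined as AEs that commence on or after the start of PF-06412528 administration". SAP 8.1.4 has the same rule. It gives a start and no end.
- **Columns.** Both sections then say "Treatment-emergent AEs will be summarized separately for the Conversion/Titration Phase and the Maintenance Phase (including up to End of Study").
- **Stopping.** Protocol 3.2.2 has the investigator act "At the final Maintenance Phase visit (Visit 4 or 5 or 6"): the instruction is to discontinue the subject's "PF-06412528 therapy and convert the subject back to their standard of care of opioid therapy".
- **End of Study.** Protocol 3 lists a "Post-Treatment Period/End of Study Period (Visit 7) lasting 1 week", and Protocol 3.3 sets it 7 ± 2 days after the last dose. SAP 2.1 has Visit 7 at 7 ± 2 days and a separate End of Study Visit 8 at 28 ± 2 days, in clinic or by telephone, for all treated subjects.
- **Serious events.** Protocol 9.4.1 adds "Serious AEs and those leading to study withdrawal will be summarized", with no phase limit.
- **Population.** Protocol 9.4 names one safety population, everyone who received at least one dose, for all safety data. Neither document defines a phase-specific set.

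**The concern.** The endpoint is about events on drug, but the Maintenance column that reports it continues after the drug has stopped and another opioid has been resumed. This matters most for withdrawal symptoms. The endpoint names them, and Protocol 1.6 gives precipitated withdrawal as the product's possible additional risk. Withdrawal on a stable dose bears on that risk. Withdrawal after stopping or reconversion is a different matter, yet both would be counted together.

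The other planned outputs do not separate them. In the Schedule of Activities, scheduled COWS (Clinical Opiate Withdrawal Scale) ratings end at Visit 6/Early Termination. Under Protocol 6.4, Visit 7 has only the AE and suicidality assessments, so scheduled capture of later withdrawal is through AE reports. Discontinuation counts by phase (SAP 8.1.1) and exposure by phase (SAP 8.1.10) do not split events by timing relative to the last dose.

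At stake is the reported percentage for the primary safety endpoint, and whether a reader can interpret it.

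**Working it through.** **1. The plan's own durations.** Inputs are the Schedule of Activities days for the four titration paths.

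- Stable-dose visit (3a to 3d): Day 7, 14, 21 or 28. Visit 4: Day 21, 28, 35 or 42. Visit 6: Day 49, 56, 63 or 70. Visit 7: Day 56, 63, 70 or 77.
- Treatment Period: 49/7 = 7 weeks to 70/7 = 10 weeks. This reproduces the 7 to 10 weeks in Protocol 3.2.
- Maintenance from the stable-dose visit to Visit 6: 49 − 7 = 42 days = 6 weeks on every path. This reproduces the stated 6 weeks. From Visit 4 it would be 49 − 21 = 28 days, which does not.
- Visit 6 to Visit 7: 56 − 49 = 7 days.

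Maintenance is therefore counted from the stable-dose visit below.

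**2. Off-drug share of the column**, in nominal days. Share = follow-up days / (Maintenance days + follow-up days).

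| Case | On drug | Off drug | Share |
|---|---|---|---|
| Visit 6 finisher, protocol | 42 | 7 | 7/49 = 14.3% |
| Same, with the ± 2-day window on Visit 7 | 42 | 5 to 9 | 5/47 = 10.6% to 9/51 = 17.6% |
| Visit 5 finisher, protocol | 28 | 7 | 7/35 = 20.0% |
| Visit 7 waived | any | 0 | 0% |
| SAP: 6-week Maintenance, Visit 8 | 42 | 28 | 28/70 = 40.0% |

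These shares follow scheduled visits. Protocol 7.2.1.1 collects AEs until the End of Study requirements are met, but serious AEs for 28 days. Protocol 6.5 also asks for an attempt at contact at 28 days. An event could therefore still be recorded where the scheduled share is 0%.

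**3. Effect on incidence.** Assume the same constant hazard on and off drug. If incidence over 42 on-drug days is p, incidence over T days is 1 − (1 − p)^(T/42).

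- p = 20%: T = 49 gives 1 − 0.8^(49/42) = 22.9%; T = 70 gives 1 − 0.8^(70/42) = 31.1%.
- p = 10%: T = 49 gives 11.6%; T = 70 gives 16.1%.

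The documents give no event rates, so p is an illustration.

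**4. Who has Visit 7.**

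- Protocol 3.2.2: scheduled after a final visit at Visit 4, 5 or 6.
- Protocol 3.3 and 6.2.2: not needed for early leavers or for subjects whose last dose is at Visit 4.
- Protocol 6.2.1 (Visit 3d): scheduled for subjects who have not reached a stable dose, who are themselves early leavers.
- SAP 2.1: required of all treated subjects, including early leavers.

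A Visit 4 finisher thus has 0 or 7 scheduled off-drug days depending on the protocol section, and 28 under the SAP.

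**5. Subjects who never enter Maintenance.** The extension to End of Study is attached only to the Maintenance column. Post-treatment events in subjects who never left titration have no stated column.

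**6. Denominator (conditional).** Read literally, Protocol 9.4 makes all treated subjects the Maintenance denominator. Twenty subjects with an event would be 20/140 = 14.3% of the planned enrolment, against 20/100 = 20.0% if only 100 entered. The 100 is the target for at least 2 weeks in Maintenance (Protocol 9.1), not a count of entrants. The true number could lie anywhere from 100 to 140 under that plan, and at 140 the difference vanishes.

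**The case against.** A post-dose window in treatment-emergent tables is a common convention. Here it is prespecified, disclosed and identical in both documents. Adding events can raise reported incidence but cannot hide harm. The tables also show relationship to drug, and because COWS is not scheduled at Visit 7, its by-visit summary is not mixed with Visit 7 data. All of this stands, and it makes the point one of interpretability. It does not supply the missing split: COWS scores are not AE incidence, and relationship to drug does not give timing relative to the last dose.

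The SAP's Visit 8 can fairly be called a failure to follow the current protocol, whose schedule has none. Protocol 9 lets the SAP modify plans for secondary endpoints, but sends major changes to the primary endpoint or its analysis to a protocol amendment. The 40.0% and 31.1% figures therefore measure a conflict between documents, not the protocol's own rule.

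On the start of Maintenance, a reader might infer that the phase has no defined beginning. The documents do not support that. One sentence in Protocol 3.2.1 places entry at Visit 4. The last paragraph of the same section, Protocol 6.2.1 and 6.2.2, and the 42-day schedule all point to the stable-dose visit. So does Protocol 3.3, which describes subjects completing 2 weeks of Maintenance by Visit 4.

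On the denominator, a population is named, and the sponsor's reporting standards (Protocol Summary; SAP 8.1) are cited but not shown. They may already use phase entrants, so that part remains conditional.

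**Conclusion.** The mismatch is real. The Maintenance column mixes on-drug and off-drug events, the endpoint refers to the on-drug period, and no planned table isolates it. Under the protocol the off-drug share is 14.3% to 20.0% of nominal column days for Visit 6 and Visit 5 finishers. Under an assumed constant hazard, the 7-day tail moves 20% to 22.9%. The End of Study conflict between protocol and SAP, and the Visit 7 conflict within the protocol, leave the column's end inconsistent.

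Three stronger conclusions are tempting and not supported:

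- That late serious AEs are lost. They are collected for 28 days and summarised without a phase limit.
- That the Maintenance percentage is biased in a known direction. The tail raises it, an all-treated denominator would lower it, and the documents do not settle the net effect.
- That a conclusion of the study would change. There is no hypothesis test or decision rule, so power and sample size are untouched.

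The sponsor should correct this, as a matter of clear reporting of a primary endpoint.

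**What to change.** 1. In Protocol 9.4.1 and SAP 8.1.4, close the on-treatment window at a stated point tied to the last PF-06412528 dose. Put later-onset AEs in a separate post-treatment column that includes subjects who never entered Maintenance. Use as its denominator the number of subjects who had post-dose AE follow-up, or print that number beside the counts. All treated subjects would be wrong there, because some have Visit 7 waived.
2. State that the Maintenance denominator is subjects dosed in that phase, unless the sponsor's standards already say so. Keep all treated subjects for Conversion/Titration and for overall incidence.
3. Align the SAP's End of Study with the protocol, and reconcile who has Visit 7 across Protocol 3.2.2, 3.3, 6.2.1 and 6.2.2 and SAP 2.1.
4. Reconcile the sentence in Protocol 3.2.1 placing Maintenance entry at Visit 4 with that section's last paragraph and with Protocol 3.3, 6.2.1 and 6.2.2.

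**Cost:** wording in both documents and slightly more table programming. The split needs no new data: AE onset date and time (Protocol 7.2.1.1) and dosing (Protocol 5.2) are already recorded. Item 3 adds contacts only if the reconciled text asks for more than sites now do.
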